Infections	
Infections occurred in a slightly greater proportion of subjects treated with belimumab compared with placebo. Infections occurring in at least 3% of patients receiving belimumab and at least 1% more frequently than patients receiving placebo were nasopharyngitis, bronchitis, pharyngitis, cystitis, and viral gastroenteritis. Serious infections occurred in 5% of patients receiving either belimumab or placebo.
	
Exclude patients with a history of any infection requiring hospitalization, antivirals or antibiotics within 4 weeks prior to Day 0., a history of or positive test at screening for HIV, Grade 3 or 4 lymphopenia, Grade 3 or 4 IgG or IgA deficiency. Patients should be excluded for serologic evidence of Hepatitis C (positive test) and evaluated for serologic evidence of Hepatitis B (HB) infection (HbsAg and anti-HbcAb). Patients with a positive HbsAg should be
	
Monitor patients for signs and symptoms of infection, monitor laboratory values, request that patients report signs of infection. Treat infections immediately and appropriately. If patient becomes hepatitis B core antibody positive and/or develop an ALT and/or AST >2.5 x ULN, obtain quantitative hepatitis B virus DNA. If the quantitative hepatitis B virus DNA result shows detectable viral loads, then the subject must be treated immediately and appropriately.

Potential risk	Summary of data	Impact- eligibility criteria	Strategy-monitoring
		excluded. Patients who are anti-HbcAb positive should be tested for HBV DNA. If DNA test is negative, the patient is eligible for inclusion	
Progressive multifocal leukoencephalopathy	PML resulting in neurological deficits, including fatal cases, has been reported in SLE patients receiving immunosuppressant pharmacotherapy, including belimumab.		A diagnosis of PML should be considered in any subject presenting with new-onset or deteriorating neurological signs and symptoms. The subject should be referred to a neurologist or other appropriate specialist for evaluation. If PML is confirmed, consideration should be given to stopping immunosuppressant therapy. If PML is suspected, this should be immediately reported to the Medical Monitor.

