#### 4.2.2. Exclusion Criteria

A subject will not be eligible for inclusion in this study if any of the following criteria apply:

1. B-cell Therapy: Have received treatment with any B cell targeted therapy (e.g., rituximab, other anti-CD20 agents, anti-CD22 [epratuzumab], anti-CD52 [alemtuzumab], BlyS-receptor fusion protein [BR3], Transmembrane activator and calcium-modulator and cytophilin ligand interactor [TACI] Fc, or belimumab) at any time.
2. The subject has received a biologic investigational or non-investigational agent within 12 months prior to Day 0.
3. Received intravenous immunoglobulin (IVIG), plasmapheresis, hemodialysis, intravenous cyclophosphamide, or high dose prednisone and its equivalents (>60mg/day) within 6 months prior to Day 0.
4. The subject has received a non-biologic investigational agent within 2 months prior to Day 0.
5. The subject is currently participating in another clinical study or post-marketing study in which the subject is or will be exposed to an investigational agent.
6. The subject has severe lupus kidney disease (defined by proteinuria >6g/24h) within 6 months prior to the Screening visit.
7. History of a major organ transplant (eg. heart, lung, renal, liver) or hematopoietic stem cell/marrow transplant.
8. Active CNS lupus [including seizures, psychosis, organic brain syndrome, cerebrovascular accident (CVA), motor neuropathy, vasculitis] requiring medical intervention within 6 months prior to Screening visit.
9. **Infections:** Have required management of acute or chronic infections, as follows:
  - Currently on any suppressive therapy for a chronic infection (such as tuberculosis, pneumocystis, cytomegalovirus, herpes simplex virus, herpes zoster and atypical mycobacteria).
  - Hospitalisation for treatment of infection within 2 months prior to Day 0.

- Use of parenteral (IV or intramuscular [IM]) antibiotics (antibacterials, antivirals, anti-fungals, or anti parasitic agents) within 2 months prior to Day 0.
10. The subject has-IgA deficiency (IgA level <10 mg/Dl).
  11. Have a history of an anaphylactic reaction to parenteral administration of contrast agents, human or murine proteins or monoclonal antibodies.

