  12. Uncontrolled other diseases: History or clinical evidence of active significant acute or chronic diseases (i.e., cardiovascular, pulmonary, untreated hypertension, anemia, gastrointestinal, hepatic, renal, neurological, cancer, or infectious diseases) which, in the opinion of the investigator, could confound the results of the study or put the subject at undue risk.
  13. Have a planned surgical procedure, or a history of any other medical disease, or laboratory abnormalities, or conditions which would make the subject (in the opinion of the Investigator) unsuitable for the study.
  14. The subject has an abnormality on 12-lead ECG at screening which is clinically significant in the opinion of the investigator, and which could confound the results of the study. Inclusion may put the subject at undue risk.
  15. Have evidence of current drug or alcohol abuse or dependence.
  16. Aspartate aminotransferase (AST) and alanine aminotransferase (ALT)  $\geq 2x$  upper limit of normal (ULN); alkaline phosphatase and bilirubin  $>1.5xULN$  (isolated bilirubin  $>1.5ULN$  is acceptable if bilirubin is fractionated and direct bilirubin  $<35\%$ ).
  17. Have a historically positive human immunodeficiency virus (HIV) test or test positive at screening for HIV.
  18. History of or positive test at screening visit for any of Hepatitis B surface antigen (HbsAg), anti- Hepatitis B core antibody (HbcAb) or anti-hepatitis C virus antibodies (HCVAb). If only anti-HbcAb result is positive, HBV-DNA test will be performed. If hepatitis B virus (HBV)-DNA results in negative, the patient is eligible.

NOTE: For those subjects included, additional ongoing assessment is required (see Section [6.2.1.1](#)).

19. **Laboratory Abnormalities:** Have a Grade 3 or greater laboratory abnormality based on the protocol toxicity scale [[Appendix 3](#)] except for the following that are allowed:
  - Stable Grade 3 prothrombin time (PT) secondary to warfarin treatment.

- Stable Grade 3/4 proteinuria ( $\leq 6$  g/24 hour equivalent by spot urine protein to creatinine ratio allowed).
  - Stable Grade 3 hypoalbuminemia due to lupus nephritis, and not related to liver disease or malnutrition.
  - Stable Grade 3 neutropenia or stable Grade 3 white blood cell count.
20. Subjects who have evidence of serious suicide risk including any history of suicidal behavior in the last 6 months or who, in the investigator's opinion, pose a significant suicide risk.

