**Table 2 Time and Events Table**

Visit	1	2						3	4	5	6	7	8	9	10	
Day	Screening Day -30 to -1	Day 0						Day 1	Day 7	Day 14	Day 21	Day 28	Day 42	Day 56	Day 84	Discontinuation 
		Pre	0	5m	1h	6h	24h									
Informed consent 	X															
Medical History	X	X														
Demography	X															
Inclusion/Exclusion criteria	X	X 														
Complete physical examination, including Height	X															
Body weight		X														
Vital signs 	X	X	X	X	X	X	X	X	X	X	X	X	X	X	X	X
Record Concomitant Medications	X	X	X	X	X	X	X	X	X	X	X	X	X	X	X	X
Clinical Laboratory test 	X	X 					X			X		X		X	X	X
Spot urine (protein to creatinine ratio)	X															
Urine drug/alcohol screen	X															
HIV, Hepatitis B, C 	X															
Pregnancy test (women) 	X	X 										X			X	X
Chest X ray	X															
12 lead ECG	X	X 					X								X	X
Biological Markers 	X 	X								X		X	X	X	X	
Blood PK sampling		X		X	X	X	X	X	X	X	X	X	X	X	X	

Visit	1	2						3	4	5	6	7	8	9	10	
Day	Screening Day -30 to -1	Day 0						Day 1	Day 7	Day 14	Day 21	Day 28	Day 42	Day 56	Day 84	Discontinuation 
		Pre	0	5m	1h	6h	24h									
AE/SAE Review 	X	X	X	X	X	X	X	X	X	X	X	X	X	X	X	X
Admission to Unit		X 														
Dosing			X													
Discharge							X 									
Outpatient Visit	X							X	X	X	X	X	X	X	X	X

1. Each subject must sign an informed consent form prior to undergoing any Screening assessments.
2. Clinical laboratory test at screening visit will be used for inclusion/exclusion criteria check.
3. Vital signs include temperature, sitting blood pressure and heart rate. Pulse rate could be used to replace heart rate monitoring if subject has regular sinus rhythm.
4. Clinical Laboratory test include hematology, chemistry and urinalysis (including C-reactive protein [CRP] and Erythrocyte Sedimentation Rate on screening). ALT and/or AST elevations of greater than 2.5 x ULN will require additional Hepatitis B assessment, see Section 6.2.1.1. For pre-dose safety lab monitoring including urine pregnancy test and 12 lead ECG, it's recommended to be done on day 0 or within 48 hours prior to day 0 if site logistic management are limited on day 0 for drug dosing and intensive PK sample collection.
5. HIV antibody, Hepatitis B surface antigen, anti-HBc and Hepatitis C antibody.

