### 12.3. Appendix 3: Adverse Event and Laboratory Value Severity Grade Tables

HEMATOLOGY	GRADE 1 MILD	GRADE 2 MODERATE	GRADE 3 SEVERE	GRADE 4 POTENTIALLY LIFE-THREATENING
Hemoglobin	>9.5 – 11.0 g/Dl	>8.0 – 9.5 g/Dl	6.5 – 8.0 g/Dl	<6.5 g/Dl
Leukocytes	3000-3999/mm 	2000-2999/mm 	1000-1999/mm 	<1000/mm 
Absolute Neutrophil Count	1500-1999/mm 	1000-1499/mm 	500-999/mm 	<500/mm 
Platelets	75,000 – 99,999/mm 	50,000 – 74,999/mm 	25,000 – 49,999/mm 	<25,000/mm 
Prothrombin Time (PT)	>1.0-1.25 x ULN*	>1.25-1.5 x ULN	>1.5-3.0 x ULN	>3.0 x ULN
Partial Thromboplastin Time (PTT)	>1.0-1.66 x ULN	>1.66-2.33 x ULN	>2.33-3.0 x ULN	>3.0 x ULN
Methemoglobin	5.0-10.0 %	10.1-15.0 %	15.1-20.0 %	>20%
				(continued)

\*ULN = Upper Limit of Normal.

Modified from [DMID](#) Adult Toxicity Tables, 2001

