**12.3 Appendix 3: Adverse Event and Laboratory Value Severity Grade Tables (continued)**

CHEMISTRIES (continued)	GRADE 1 MILD	GRADE 2 MODERATE	GRADE 3 SEVERE	GRADE 4 POTENTIALLY LIFE-THREATENING
Uric Acid				
Hyperuricemia	7.5-10.0 mg/Dl	10.1-12.0 mg/Dl	12.1-15.0 mg/Dl	>15.0 mg/Dl
Liver Transferases (AST, ALT, and GGT)	1.25-2.5 x ULN	>2.5-5.0 x ULN	>5.0-10.0 x ULN	>10.0 x ULN
Alkaline Phosphatase	1.25-2.5 x ULN	>2.5-5.0 x ULN	>5.0-10.0 x ULN	>10.0 x ULN
Pancreatic Enzymes				
Amylase	>1.0-1.5 x ULN	>1.5-2.0 x ULN	>2.0-5.0 x ULN	>5.0 x ULN
Pancreatic amylase	>1.0-1.5 x ULN	>1.5-2.0 x ULN	>2.0-5.0 x ULN	>5.0 x ULN
Lipase	>1.0-1.5 x ULN	>1.5-2.0 x ULN	>2.0-5.0 x ULN	>5.0 x ULN
Hypoglobulinemia (IgG)*	550-700 mg/Dl	400-549 mg/Dl	250-399 mg/Dl	<250 mg/Dl
				(continued)

\*[Eibl, 1995; Goldfarb, 2001; Yamini, 2001].

Modified from DMID Adult Toxicity Tables, 2001

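### Protocol Table 1 excludes Grade 3–4 lymphopenia, but no rule in Section 4.2.2 or Appendix 3 objectively excludes isolated severe lymphopenia, or lymphopenia with a stable Grade 3 white cell count

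*Protocol*

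**What the plan says.** Protocol Section 3.4, Table 1, has a column for the effect of each risk on eligibility. In the Infections row that column lists "Grade 3 or 4 lymphopenia, Grade 3 or 4 IgG or IgA deficiency" among the reasons to exclude a patient.

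The operative list is Section 4.2.2, with 22 exclusion criteria. The parts that bear on this point are:

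- **Criterion 10** excludes IgA below 10 mg/dL.
- **Criterion 12** covers significant active disease that, in the investigator's opinion, could confound results or put the subject at undue risk.
- **Criterion 13** covers "laboratory abnormalities, or conditions which would make the subject (in the opinion of the Investigator) unsuitable for the study".
- **Criterion 19** is the only graded laboratory exclusion: "Have a Grade 3 or greater laboratory abnormality based on the protocol toxicity scale", which is Appendix 3. Its listed exceptions include "Stable Grade 3 neutropenia or stable Grade 3 white blood cell count".

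The Hematology table of Appendix 3 grades seven items: hemoglobin, leukocytes, "Absolute Neutrophil Count", platelets, PT, PTT and methemoglobin. The later Appendix 3 tables include a row for low IgG.

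Table 2, footnote 2, fixes the data used for eligibility: "Clinical laboratory test at screening visit will be used for inclusion/exclusion criteria check". Section 6.1.1 includes the white cell differential in the screening hematology.

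**The concern.** Table 1 presents the lymphopenia exclusion as a safeguard against infection. Section 3.4 counts non-opportunistic infection among the identified risks of the drug. The condition is foreseeable in this population: lymphopenia is one of the hematologic features in the ACR classification (Appendix 2), and Section 4.2.1 permits background corticosteroids and immunosuppressants.

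Sites decide eligibility from Section 4.2.2, and Section 4.2 allows no deviation from the criteria as specified. If the criteria do not contain the safeguard, a site can follow the protocol exactly and still enrol a subject whom Table 1 says is excluded. Sites in this multicenter study could also treat the same screening result differently. What is at stake is subject safety and uniform enrolment, not the pharmacokinetic estimates.

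**Working it through.** The plan gives no figure to reproduce. The check sets the texts side by side and then tests whether neighbouring rows of Appendix 3 do the work of the missing one.

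**Step 1. How each item in the Table 1 clause reaches an exclusion criterion.**

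| Item in Table 1 | Named in 4.2.2? | Graded in Appendix 3? | Objective rule |
|---|---|---|---|
| Grade 3–4 IgG deficiency | No, enters through criterion 19 | Yes: Grade 3 is 250–399 mg/dL, Grade 4 is below 250 mg/dL | Yes |
| Grade 3–4 IgA deficiency | Yes, criterion 10 | No | Yes, below 10 mg/dL, but tied to no grade |
| Grade 3–4 lymphopenia | No (0 of 22 criteria) | No (0 of 7 Hematology rows, none elsewhere) | None specific to lymphocytes |

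IgG is fully implemented. IgA has a usable cut-off, but nothing in the documents shows that 10 mg/dL corresponds to Grade 3 or 4, so the grade wording in Table 1 has no referent there. Lymphopenia has neither a criterion nor a grade.

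**Step 2. What the leukocyte row covers.** Appendix 3 sets leukocytes at Grade 3 for 1000–1999/mm³ and Grade 4 below 1000/mm³. Criterion 19 with its exceptions therefore excludes a total count below 1000/mm³, and a count of 1000–1999/mm³ that is not stable. Lymphocytes are part of the total, so some subjects with low lymphocytes are caught this way. A total of 2000/mm³ or more is not excluded, and neither is a stable Grade 3 total.

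**Step 3. Whether leukocytes and neutrophils together bound lymphocytes.** Lymphocytes cannot exceed white cells minus neutrophils. The neutrophil grades are: Grade 1, 1500–1999; Grade 2, 1000–1499; Grade 3, 500–999; Grade 4, below 500/mm³. Three illustrative counts (all per mm³):

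| White cells | Grade | Neutrophils | Grade | Upper bound on lymphocytes |
|---|---|---|---|---|
| 4000 | none | 3800 | none | 4000 − 3800 = 200 |
| 2100 | 2 | 2000 | none | 2100 − 2000 = 100 |
| 1600 | 3, allowed if stable | 1500 | 1 | 1600 − 1500 = 100 |

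Criterion 19 excludes none of the three on these rows. The two rows set no lower limit on lymphocytes.

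**Step 4. What remains.** For isolated low lymphocytes (total count 2000/mm³ or more), or low lymphocytes with a stable Grade 3 total, only criteria 12 and 13 can exclude. Both depend on the investigator's opinion.

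**The case against.** The strongest reply is that Table 1 is a summary and Section 4.2.2 governs, so the operative rule is clear and the mismatch is editorial. It is fair to call this an alignment error. But if Section 4.2.2 governs, the stated safeguard is absent. If Table 1 binds, its grade has no definition. Neither reading gives sites a rule. The sponsor has treated this kind of mismatch as worth amending: the Amendment 01 change log (Appendix 4) gives consistency with the benefit-risk section as the reason for adding criterion 22.

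A reader might infer that lymphopenia is left entirely to discretion. That goes too far. As step 2 shows, the leukocyte row objectively excludes the lowest total counts and unstable Grade 3 counts. The gap is confined to the two situations in step 4.

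A reader might also infer that the SAP's hematology toxicity tables are deficient for lacking a lymphocyte grade. The documents do not support that. SAP Section 11.6 promises grading only when possible, and hematology values and changes from baseline are tabulated regardless.

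The examples are constructed: neutrophils make up about 94–95% of white cells in each (3800/4000 = 95.0%, 2000/2100 = 95.2%, 1500/1600 = 93.8%). They show that the gap can occur, not how often. That objection stands. So does the point that exposure is limited: one dose at an approved level, about 20 subjects, and review of adverse events and infection symptoms at every visit.

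**Conclusion.** The inconsistency is real and lies in the current text. Table 1 states an exclusion for Grade 3–4 lymphopenia. The criteria and grading scale do not deliver it for isolated severe lymphopenia, or for lymphopenia with a stable Grade 3 white cell count.

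Its size is small. The documents give neither a Grade 3 or 4 lymphocyte cut-off nor a frequency, so the number of subjects affected cannot be derived. Calling the illustrative bounds of 100–200/mm³ severe is an assumption until the sponsor sets cut-offs. The ACR lymphocyte figure in Appendix 2 is a classification feature of the disease and cannot serve as a toxicity grade. PK, PD and sample size are unaffected. This is a minor safety and eligibility correction, worth making because it is cheap and concerns an identified risk.

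**What to change.** Do one of the following:

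- Add a lymphocyte row to Appendix 3, with Grade 1–4 cut-offs set by the sponsor's clinical team, so that criterion 19 applies the exclusion. The exceptions in criterion 19 form a closed list that does not name lymphocytes, so they need no change. SAP laboratory grading uses Appendix 3, so the new row would also carry into the toxicity displays.
- Add an equivalent numeric lymphocyte exclusion to Section 4.2.2. This is narrower and leaves the grading scale as it is.

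In the same Table 1 clause, replace the grade wording for IgA with the cut-off in criterion 10.

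The cost is a short protocol amendment and possibly a few more screen failures. No new blood test is needed, because the white cell differential is already collected at screening.

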## 4. STUDY POPULATION

### 4.1. Number of Subjects

Approximately 20 subjects will be enrolled to guarantee no less than 12 subjects complete dosing and critical assessments.

### 4.2. Eligibility Criteria

Specific information regarding warnings, precautions, contraindications, adverse events, and other pertinent information on the GlaxoSmithKline (GSK) investigational product (IP) or other study treatment that may impact subject eligibility is provided in the IB/IB supplement(s), product label, and other pertinent documents.

Deviations from inclusion and exclusion criteria are not allowed because they can potentially jeopardize the scientific integrity of the study, regulatory acceptability or subject safety. Therefore, adherence to the criteria as specified in the protocol is essential.

#### 4.2.1. Inclusion Criteria

A subject will be eligible for inclusion in this study only if all of the following criteria apply:

1. Subjects who give consent to this study participation and sign informed consent form.
2. Subjects at least 18 years of age inclusive at screening visit.
3. **SLE Classification:** Have a clinical diagnosis of SLE according to the American College of Rheumatology (ACR) classification criteria, with 4 or more of the 11 ACR criteria present, serially or simultaneously during any interval or observation. [Tan, 1982; Hochberg, 1997] (See [Appendix 2](#)).
4. **SLE Treatment:** Be on either no SLE medication or a stable SLE treatment regimen of any medication (alone or in combination) for a period of at least 2 months prior to Day 0.
  - Corticosteroids (prednisone or prednisone equivalent, up to 40 mg/day)
  - Immunosuppressive or immunomodulatory agents including methotrexate, azathioprine, leflunomide, mycophenolate (including mycophenolate mofetil, mycophenolate mofetil hydrochloride, and mycophenolate sodium), mizoribine, calcineurin inhibitors (e.g., tacrolimus, cyclosporine), sirolimus, oral cyclophosphamide, 6-mercaptopurine, or thalidomide.
  - Anti-malarials (e.g., hydroxychloroquine, chloroquine, quinacrine).
  - Non-steroidal anti-inflammatory drugs (NSAIDs)

## NOTE:

- For those subjects on alternating day doses of steroids, use the average of 2 daily doses to calculate the average daily steroid dose.
  - Low dose prednisone ( $\leq 15$ mg prednisone or equivalent) regular tapering will be acceptable as stable SLE treatment.
5. The subjects with positive test for anti-nuclear antibody (ANA) or anti-dsDNA serum antibody.
  6. Males and females. A female subject is eligible to enter the study if at least one of the following conditions apply:
    - Not pregnant or nursing;
    - Of non-childbearing potential (i.e., women who had a hysterectomy, are postmenopausal which is defined as 1 year without menses, have both ovaries surgically removed or have current documented tubal ligation); or
    - Of childbearing potential (i.e., women with functional ovaries and no documented impairment of oviductal or uterine function that would cause sterility). This category includes women with oligomenorrhoea [even severe], women who are perimenopausal or have just begun to menstruate. These women must have a negative serum pregnancy test at screening, and agree to 1 of the following:
      - Complete abstinence from penile-vaginal intercourse, when this is the female's preferred and usual lifestyle, from 2 weeks prior to administration of the 1st dose of IP until study complete; or
      - Consistent and correct use of 1 of the following acceptable methods of birth control for 1 month prior to the start of the IP and for 16 weeks after the last dose of IP:
        - Any intrauterine device (IUD) or intrauterine system (IUS) with a documented failure rate of less than 1% per year.
        - Oral contraceptives.
        - Double barrier method with vaginal spermicidal agent: Condom and an occlusive cap (cervical cap/vault or diaphragm) with a vaginal spermicidal agent (foam/gel/film/cream/suppository).
        - Implants of etonogestrel or levonorgestrel;
        - Estrogenic vaginal ring;
        - Injectable progesterone;
        - Percutaneous contraceptive patch;
        - Male partner who is sterile prior to the female subject's entry into the study and is the sole sexual partner for the female subject.

Note: MMF and other forms of mycophenolate affect the metabolism of oral contraceptives and may reduce their effectiveness. As such, women receiving mycophenolate who are using oral contraceptives for birth control should employ an additional method (e.g., barrier method).

7. Based on single or averaged QTc values of triplicate ECGs obtained over a brief recording period:
  - [QTcB or QTcF] <450 msec; or
  - QTcB or QTcF <480 msec in subjects with Bundle Branch Block.

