### 4.2.3. Contraception Requirements

#### 4.2.3.1. Female Subjects

Female subjects of childbearing potential must not become pregnant and so must be sexually inactive by abstinence or use contraceptive methods with a failure rate of  $<1\%$ . Female subjects of childbearing potential with same sex partners (when this is their preferred and usual lifestyle) are not required to be abstinent or to use contraception.

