#### Contraceptive Methods with a Failure Rate of $<1\%$

- Oral contraceptive, either combined or progestogen alone
- Injectable progestogen
- Implants of etonogestrel or levonorgestrel
- Estrogenic vaginal ring
- Percutaneous contraceptive patches
- Intrauterine device (IUD) or intrauterine system (IUS) that meets the  $<1\%$  failure rate as stated in the product label
- **Documented** male partner sterilization prior to **the female subject's entry** into the study, and this male is the sole partner for that subject. For this definition, "documented" refers to the outcome of the investigator's/designee's review of the

subject's medical history for study eligibility, as obtained via a verbal interview with the subject or from the subject's medical records.

- Male condom combined with one of the contraceptive options below:
  - Contraceptive subdermal implant
  - Intrauterine device or intrauterine system
  - Combined estrogen and progestogen oral contraceptive
  - Injectable progestogen
  - Contraceptive vaginal ring Percutaneous contraceptive patches

**NOTE:** These allowed methods of contraception are only effective when used consistently, correctly and in accordance with the product label. The investigator is responsible for ensuring subjects understand how to properly use these methods of contraception.

- MMF and other forms of mycophenolate affect the metabolism of oral contraceptives and may reduce their effectiveness. As such, women receiving mycophenolate who are using oral contraceptives for birth control should employ an additional method (e.g., barrier method).

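### Inclusion criterion 6 makes being neither pregnant nor nursing only one of three alternatives, so a nursing woman can qualify; its contraceptive list also needs aligning with Section 4.2.3.1

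*Protocol*

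**What the plan says.** Protocol Section 4.2.1 opens with a cumulative rule: "A subject will be eligible for inclusion in this study only if all of the following criteria apply". Within criterion 6 the rule for women is different: "A female subject is eligible to enter the study if at least one of the following conditions apply". Three conditions follow, with the word *or* before the last:

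1. "Not pregnant or nursing".
2. Non-childbearing potential: hysterectomy, postmenopausal, both ovaries removed, or documented tubal ligation.
3. Childbearing potential, with a negative serum pregnancy test at screening and agreement either to abstinence until the study is complete or to one of eight listed methods until 16 weeks after the last dose.

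One of the eight methods is "Double barrier method with vaginal spermicidal agent", meaning a condom plus an occlusive cap or diaphragm.

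Section 4.2.3.1 adds its own rule. Women of childbearing potential "must be sexually inactive by abstinence or use contraceptive methods with a failure rate of" less than 1%. A condom appears in its list only as "Male condom combined with one of the contraceptive options below", and those options are implant, IUD/IUS, combined pill, injectable, ring or patch.

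Two other places bear on who may enter. Section 4.2 refers sites to product information "that may impact subject eligibility is provided in the IB/IB supplement(s), product label, and other pertinent documents". Exclusion 13 bars subjects with a medical history, laboratory abnormalities "or conditions which would make the subject (in the opinion of the Investigator) unsuitable for the study".

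**The concern.** The first condition shows that the authors wanted nursing women kept out. Because it is one alternative among three, it does not bind a woman who satisfies either of the others. Section 4.2 allows no deviations and asks sites to follow the criteria as specified, so the wording itself decides eligibility.

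What is at stake is whether the protocol, rather than each investigator's judgement, keeps a nursing woman from receiving the 10 mg/kg dose. Such a woman would meet every inclusion criterion as written, so the listing of inclusion/exclusion deviations planned in SAP Section 5.1 would have no reason to show her.

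The contraceptive lists raise a smaller issue: two current sections give sites different answers on double barrier.

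**Working it through.** The plan gives no figure on this point. The check is logical, followed by a comparison of the two method lists.

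**Eligibility logic.** Let
- A = neither pregnant nor nursing,
- B = non-childbearing potential,
- C = childbearing potential, negative serum test, and agreement to abstinence or a listed method.

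Criterion 6 as written is A or B or C. The evident intent is A and (B or C). The pregnancy test is assumed accurate.

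| Woman | A | B | C | As written | Intended |
|---|---|---|---|---|---|
| Not pregnant, not nursing, non-childbearing | yes | yes | no | in | in |
| Not pregnant, not nursing, childbearing, agrees | yes | no | yes | in | in |
| Not pregnant, not nursing, childbearing, does not agree | yes | no | no | in | out |
| Nursing, non-childbearing | no | yes | no | **in** | **out** |
| Nursing, not pregnant, childbearing, agrees | no | no | yes | **in** | **out** |
| Nursing, not pregnant, childbearing, does not agree | no | no | no | out | out |
| Pregnant, nursing or not | no | no | no | out | out |

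The rows are logical cases and say nothing about how many women fall in each. The two bold rows are the defect. The third row also differs, but Section 4.2.3.1 separately requires abstinence or contraception of every woman of childbearing potential, so she is stopped there.

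**Search for another bar on nursing.** Exclusions 1 to 22 do not name it. Section 4.2.3.1 deals with contraception only. The screening and pre-dose lists (Sections 6.1.1 and 6.1.2) contain pregnancy tests but no item naming nursing. What remains is exclusion 13, which permits exclusion without requiring it, and the Investigator's Brochure or label, whose content on nursing is not given in the protocol or SAP.

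**Method lists.** Of the eight methods in criterion 6, seven have a counterpart in Section 4.2.3.1: IUD/IUS, oral contraceptive, implant, ring, injectable, patch and sterile male partner. The eighth, double barrier with spermicide, has none (8 − 7 = 1). In the other direction, Section 4.2.3.1 adds only a condom used together with a method that criterion 6 already accepts.

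**End of abstinence.** Section 4.4 defines a subject as complete after all sessions, including follow-up, and the last scheduled visit in Table 2 is Day 84. Read that way, the abstinence commitment ends at Day 84, while the other methods run to 16 × 7 = 112 days. The difference is 112 − 84 = 28 days. If completion is instead taken to include pregnancy follow-up to week 16, it is 0 days.

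**The case against.** The strongest reply is that this is a misplaced connector whose intent any site would recognise. Read literally, the criterion leaves its own contraception terms idle for any woman who is neither pregnant nor nursing, which cannot have been meant. Investigators can use exclusion 13, and Section 4.2 sends them to the Investigator's Brochure and label. The risk discussion in Section 3.4 states no hazard from lactation, so harm is not shown. All of this is fair, and it limits the seriousness of the point. It does not make the criterion exclude a nursing woman: discretion is not a rule, and the outside sources cannot be checked here.

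On double barrier, the reply largely succeeds. Both sections apply, so the stricter list in Section 4.2.3.1 already disallows the method, and what remains is a mismatch in the text.

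On abstinence, Table 2 (footnote 6) provides home-kit pregnancy testing with telephone reporting after Day 84, and Section 7.2 requires pregnancies to be reported for 16 weeks after the last dose. The window is therefore monitored, and Section 4.2.3.1 sets no early stop date of its own.

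Several stronger readings are tempting but not supported:
- *Pregnant women could enter.* They could not; the third condition requires a negative test.
- *Women of childbearing potential could enter without contraception.* Section 4.2.3.1 prevents it.
- *Double barrier breaches the 1% limit.* Neither document gives a failure rate for it; only its absence from the allowed list can be shown.
- *Study completion is undefined.* Section 4.4 gives a definition of subject completion.
- *The sterile-partner items conflict because only Section 4.2.3.1 asks for documentation.* That section accepts a verbal interview as documentation, so the difference is slight.

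**Conclusion.** The nursing point stands as a drafting defect in a stated eligibility rule. As worded, criterion 6 admits a nursing woman of non-childbearing potential, and a nursing woman of childbearing potential with a negative test and agreed abstinence or contraception. Nothing else in the protocol names nursing as a bar. This should be corrected.

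The double-barrier mismatch is real but secondary, because the stricter section governs. The end of abstinence is an optional clarification.

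Reach is uncertain. Section 1.1.1 puts women at about 90% of SLE patients. If enrolment follows that share, criterion 6 would govern about 0.9 × 20 = 18 of the roughly 20 planned subjects. How many would be nursing or relying on double barrier is not stated and may be none. The conclusion rests on reading the connector literally and on the Investigator's Brochure and label being unavailable. No endpoint, sample size, visit or analysis is affected.

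**What to change.** - **Main change.** Reword criterion 6 so that a woman must be neither pregnant nor nursing AND must be either of non-childbearing potential, OR of childbearing potential with a negative serum test and agreement to abstinence or contraception.
- **Alignment.** Delete double barrier from criterion 6 and use one method list for both sections, most simply by having criterion 6 refer to Section 4.2.3.1.
- **Optional.** State that abstinence runs to 16 weeks after the dose, as for the other methods and the pregnancy follow-up.

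The cost is amendment wording with the IRB/IEC approval that Section 10.2 requires. A woman relying on double barrier would need a listed method or abstinence. The SAP analyses need no change.
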